Clinical Trial Protocol

Document Number: c21116620-03

EudraCT No.:	2017-004899-62	
BI Trial No.:	1405-0001	
BI Investigational Product:	BI 1323495	
Title:	Safety, tolerability, pharmacokinetics, and pharmacodynamics of single rising oral doses of BI 1323495 in healthy male subjects (single-blind, partially randomised, placebo-controlled parallel group design)	
Lay Title:	This study in healthy men tests how different doses of BI 1323495 are taken up in the body and how well they are tolerated.	
Clinical Phase:	I	
Trial Clinical Monitor:		
Principal Investigator:		
Status:	Final Protocol (Revised Protocol (based on global amendment 2))	
Version and Date:	Version: 3.0	Date: 28 August 2018
Page 1 of 77		
Proprietary confidential information		
© 2018 Boehringer Ingelheim International GmbH or one or more of its affiliated companies. All rights reserved.		
This document may not - in full or in part - be passed on, reproduced, published or otherwise used without prior written permission		

CLINICAL TRIAL PROTOCOL SYNOPSIS

Name of company: Boehringer Ingelheim		Tabulated Trial Protocol		
Name of finished product: Not applicable				
Name of active ingredient: BI 1323495				
Protocol date: 24 April 2018	Trial number: 1405-0001		Revision date: 28 August 2018	
Title of trial: Safety, tolerability, pharmacokinetics, and pharmacodynamics of single rising oral doses of BI 1323495 in healthy male subjects (single-blind, partially randomised, placebo-controlled parallel group design)				
Principal Investigator:				
Trial site:				
Clinical phase:	I			
Objectives:	To investigate safety, tolerability, pharmacokinetics, and pharmacodynamics following single rising oral doses of BI 1323495			
Methodology:	Single-blind, partially randomised within dose groups, placebo-controlled, parallel-group			
No. of subjects:				
total entered:	64*			
each treatment:	8 per dose group (6 on active drug and 2 on placebo) * Additional subjects may be entered to allow testing of additional doses on the basis of experience gained during the trial conduct (e.g. preliminary PK data), provided the planned and approved highest dose will not be exceeded and none of the stopping criteria apply. Thus, the actual number of subjects entered may exceed 64, but will not exceed 80 subjects.			
Diagnosis:	Not applicable			
Main criteria for inclusion:	Healthy male subjects, age of 18 to 45 years (inclusive), body mass index (BMI) of 18.5 to 29.9 kg/m ² (inclusive)			
Test products:	BI 1323495 film-coated tablets (dose strengths mg) dose: mg as single dose			
mode of admin.:	Oral with 240 mL of water after an overnight fast of at least 10 h			
Comparator products:	Matching placebo tablets			
dose:	Not applicable			
mode of admin.:	Oral with 240 mL of water after an overnight fast of at least 10 h			
Duration of treatment:	one single dose			

Proprietary confidential information © 2018 Boehringer Ingelheim International GmbH or one or more of its affiliated companies

Name of company: Boehringer Ingelheim		Tabulated Trial Protocol			
Name of finished product: Not applicable					
Name of active ingredient: BI 1323495					
Protocol date: 24 April 2018	Trial number: 1405-0001		Revision date: 28 August 2018		
Criteria for pharmacokinetics: Secondary endpoints: AUC and C					
Criteria for pharmacodynamics:					
Criteria for safety: Primary endpoint to assess safety and tolerability of BI 1323495 is the number [N (%)] of subjects with drug-related adverse events. Further criteria of interest: AEs including clinically relevant findings from the physical examination, safety laboratory tests, 12-lead electrocardiogram (ECG), continuous ECG monitoring, vital signs (blood pressure [BP], pulse rate [PR]).					
Statistical methods: Descriptive statistics will be calculated for all endpoints. Dose proportionality of BI 1323495 will be explored using a regression model. A 95% confidence interval (CI) for the slope will be computed.					

A 2D grid of horizontal and vertical lines. The grid consists of a main rectangular frame defined by thick black lines, with a smaller rectangular hole in the lower-left quadrant. The grid is composed of thin black lines, with the main frame having a bounding box of approximately [111, 111, 889, 885] and the hole having a bounding box of approximately [111, 111, 889, 885]. The grid is centered on the page.

TABLE OF CONTENTS

TITLE PAGE	1
CLINICAL TRIAL PROTOCOL SYNOPSIS	2
TABLE OF CONTENTS	6
ABBREVIATIONS	10
1. INTRODUCTION.....	12
1.2 DRUG PROFILE	13
1.2.2 Toxicology.....	14
1.2.5 Clinical experience in humans	18
1.2.6 Drug product	19
2. RATIONALE, OBJECTIVES, AND BENEFIT - RISK ASSESSMENT	20
2.1 RATIONALE FOR PERFORMING THE TRIAL	20
2.1.1 Starting dose	20
2.1.2 Maximum dose and dose escalation	21
2.1.3 Conclusion	22
2.2 TRIAL OBJECTIVES.....	22
2.3 BENEFIT - RISK ASSESSMENT	23
2.3.1 Procedure-related risks	23
2.3.2 Drug-related risks	23
2.3.2.5 Drug-induced liver injury	25
2.3.3 Safety measures	25

gMean	Geometric mean
HPC	Human Pharmacology Centre

Proprietary confidential information © 2018 Boehringer Ingelheim International GmbH or one or more of its affiliated companies

HR	Heart rate
IB	Investigator's brochure
IC ₅₀	Half-maximal inhibitory concentration
IEC	Independent Ethics Committee
IRB	Institutional Review Board
ISF	Investigator site file
LC-MS/MS	Liquid chromatography with tandem mass spectrometry
MedDRA	Medical Dictionary for Regulatory Activities
MRSD	Maximum recommended starting dose
MRT _{po}	Mean residence time of the analyte in the body after oral administration
NOA	Not analysed
NOAEL	No observed adverse effect level
NOR	No valid result
NOS	No sample available
PD	Pharmacodynamic(s)
PK	Pharmacokinetic(s)
PKS	Pharmacokinetic set
PR	Pulse rate
QT	Time between start of the Q-wave and the end of the T-wave in an electrocardiogram
QTc	QT interval corrected for heart rate using the method of Fridericia (QTcF) or Bazett (QTcB)
REP	Residual effect period
SAE	Serious adverse event
SCR	Screening
ss	(at) steady state
TMF	Trial master file
t _{1/2}	Terminal half-life of the analyte in plasma
t _{max}	Time from (last) dosing to the maximum measured concentration of the analyte in plasma
t _z	Time of last measurable concentration of the analyte in plasma
TDMAP	Trial Data Management and Analysis Plan
TSAP	Trial statistical analysis plan
ULN	Upper limit of normal
V _{ss}	Volume of distribution at steady state
V _{z/F}	Apparent volume of distribution during the terminal phase after extravascular administration

1. INTRODUCTION

In this study, BI 1323495 will be given to humans for the first time. Safety, tolerability, pharmacokinetics, and pharmacodynamics of single rising doses of BI 1323495 will be investigated.

1.2 DRUG PROFILE

For details on nonclinical pharmacology refer to the current version of the Investigator's Brochure (IB, [c21238478-01](#)).

1.2.2 Toxicology

Details on toxicology results are provided in the current version of the IB ([c21238478-01](#)).

1.2.5 Clinical experience in humans

To date, no experience with BI 1323495 is available in human.

1.2.6 Drug product

Further details are given in the Investigator's Brochure
([c21238478-01](#)).

2. RATIONALE, OBJECTIVES, AND BENEFIT - RISK ASSESSMENT

2.1 RATIONALE FOR PERFORMING THE TRIAL

As a transition from preclinical investigations to clinical development in this first-in-man trial, safety, tolerability, pharmacokinetics, and pharmacodynamics of BI 1323495 will be assessed in healthy male volunteers using single rising oral doses in order to provide the basis for a potential ongoing clinical development of BI 1323495

Healthy male subjects aged 18 - 45 years will be recruited for this study. They provide a relatively stable physiological, biochemical, and hormonal basis (steady state) for studying drug effects, they show no disease-related variation, and they are not taking concomitant medication.

Within each dose group, all actively treated individuals will receive the same BI 1323495 dose. The next higher dose will only be administered (to the next group) if the treatment in the preceding dose groups was safe and showed acceptable tolerability.

It is intended to investigate the following dose levels of BI 1323495 in this trial:

mg.

The background for this dose selection is described in the following paragraphs.

2.1.1 Starting dose

It is best practice to use different methods for dose selection and to take a starting dose at the lower end of the dose range if different methods give different estimates (err on the side of caution).

Applying the respective calculation as given in the US FDA Guidance for Industry 'Estimating the Maximum Safe Starting Dose in Initial Clinical Trials for Therapeutics in Adult Healthy Volunteers' ([R06-1037](#)), and assuming a no adverse effect level (NOAEL) of a maximum recommended starting dose (MRSD) as high as could be selected based on the 4 week toxicology data A detailed description of the derivation of the MRSD can be found in the IB ([c21238478-01](#)).

The therapeutic human dose of BI 1323495 is predicted to be (see [Section 1.2.4](#)). The starting dose should be sub-therapeutic; therefore it should be lower than the expected therapeutic dose. Application of a factor of 10 to the predicted therapeutic human dose results in a maximum recommended safe starting dose of approximately in humans.

A single dose of is predicted to achieve exposures of which is well below expected therapeutic exposures of providing even sufficient margin to therapeutic exposures should the bioavailability be higher than the predicted (see [Section 1.2.4](#)).

Finally, another commonly used NOAEL-based approach, following ICH guidance M3 (R2), is to use a fraction of the NOAEL, e.g. 1/50 or 1/100 ([R09-1400](#)). Based on the NOAEL of body weight and assuming a body weight of 50 kg the starting dose would be in the range of

Taken together, different approaches give a starting dose in the range of

is finally considered as an appropriate and safe starting dose based on:

- Published experience from clinical trials with administration of and achieving higher levels of target engagement over longer periods of time not revealing any mode of action-related adverse effects ([Section 1.2.5](#));
- the toxicological profile of BI 1323495 in relevant animal models ([Section 1.2.2](#));
- the effect being reversible;
- only single doses being applied;
- lower peak exposures being expected in

Therefore at expected exposures achieved with this dose, is not expected to trigger any relevant or unacceptable biological activity ([Section 1.2.5](#)).

2.1.2 Maximum dose and dose escalation

As stated above, a minimum daily dose of about may be required to achieve therapeutic systemic exposure of BI 1323495. Nevertheless, it is planned to explore higher doses / exposures in this trial for several reasons. Subsequent clinical trials in patients might show that required therapeutic doses and exposures are significantly higher than predicted. Also, higher doses / exposures might be required for more severe disease states, for induction vs. maintenance treatment, and for other indications. So while higher doses and exposures might still be well tolerated they provide a larger magnitude of therapeutic effects. Further, testing of doses higher than is also reasonable to compensate for any bioavailability and half-life being lower/shorter than expected. If, for example, bioavailability was significantly less than the predicted (see [Section 1.2.4](#)), the therapeutic dose could eventually turn out to be several fold higher than currently predicted. And even if the therapeutic dose turns out to be as low as higher than therapeutic doses / exposures are typically explored in the well-controlled clinical environment of first-in-man trials to provide a safety margin for following trials, e.g. drug-drug-interaction trials, trials with patients with impaired excretion function, etc., where substantial increases in exposure may be seen.

The maximum human exposure to BI 1323495 in this trial will be limited to nM for C_{max} and nM*h for AUC₀₋₂₄.

This provides a safety margin with a factor of at least 24 (C_{max}) and 21 (AUC) to the exposures achieved after 4-week administration of /kg in the most sensitive species,

These findings are not expected after a single administration of BI 1323495 at doses achieving exposure levels well below exposures
With respect to the NOAEL in the 4-week toxicity study
the maximum human exposure defined above provides safety factors of 16 and 10, respectively. The given safety margins refer to the lower exposures
With respect to the NOAEL in the 4-week toxicity study
this maximum human exposure provides safety margins of approximately 28 and 34, respectively. On the other hand, the defined acceptable maximum exposure for this trial provides a margin of factor (C_{max}) and (AUC) above the expected therapeutic exposure to explore the therapeutic potential of the compound.

For the present trial, a maximum dose of has been selected, but this dose will only be administered if, based on interim PK measurements (see [Section 7.3.4](#)), individual C_{max} or AUC₀₋₂₄ values at a lower dose or predicted geometric mean values of C_{max} or mean AUC₀₋₂₄ do not exceed exposure limits defined above. Otherwise dose escalation will be stopped at lower doses. Based on the preclinical safety profile of BI 1323495, these exposure limits are anticipated to be safe and well tolerated.

The escalation schedule has been chosen in a way that a shallow escalation will be applied for the higher dose levels with a factor not greater than 1.5. This dose escalation is considered to be adequate and safe, particularly when the selected exposure safety margins are taken into consideration.

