2.3.3 Safety measures

- Dose selection was based on a sound preclinical package including 4 week toxicological studies (see [Section 1.2.3](#)) and non-clinical pharmacology data ([Section 1.2.1](#)).

Careful selection of starting dose as described in [Section 2.1](#).

Dose escalation will be shallow with an increase of not more than 1.5 fold at the higher dose groups.

Proprietary confidential information © 2018 Boehringer Ingelheim International GmbH or one or more of its affiliated companies

- Measurement of BI 1323495 plasma concentrations and preliminary determination of PK parameters (C_{max} , AUC_{0-24} , see [Section 7.3.4](#)). For precautionary reasons, drug plasma concentrations in this healthy volunteer trial should not exceed a C_{max} of _____ or an AUC_{0-24} of _____ and will be considered as a preliminary threshold (see [Section 2.1](#)). Further dose progression would only be allowed after a safety interim analysis and filing and approval of a substantial CTP amendment.
- For safety reasons, each dose group of 8 subjects (6 on active, 2 on placebo) will be divided into three cohorts. In the 1st cohort only 2 subjects will be treated: one subject will receive active treatment, the other subject will receive placebo. If BI 1323495 treatment is safe and well tolerated in this first cohort, the following 2 subjects on active will be treated in the 2nd cohort with drug administration occurring not earlier than 24 hours after the first subject of the dose level received active treatment. The remaining 4 subjects (either active or placebo) are the third cohort and will be treated no sooner than 48 hours following the 1st cohort. Within each cohort, a time interval of at least 10 min will be maintained between administrations of study drug.

This design ensures that between first and second active dose of each dose level there is a time interval of at least 24 hours, which is expected to be sufficient to detect relevant first acute effects of BI 1323495.

- Only if the respective dose of BI 1323495 was safe and showed acceptable tolerability and if no stopping criterion was met (see [Section 3.3.4.2](#)), the next higher dose will be given at least 6 days later (referring to the 1st subject of each dose group). A documented Safety Review must take place prior to each dose escalation (see [Section 3.1](#)).
- An extensive safety laboratory will be performed (see [Section 5.2.3](#)).

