3.3.4.2 Discontinuation of the trial by the sponsor

Boehringer Ingelheim reserves the right to discontinue the trial overall or at a particular trial site at any time for any of the following reasons:

1. New toxicological findings or serious adverse events invalidate the earlier positive benefit-risk-assessment. Dose escalation will be terminated if more than 50% of the subjects at one dose level show drug-related and clinically relevant adverse events of moderate or severe intensity.

Proprietary confidential information © 2018 Boehringer Ingelheim International GmbH or one or more of its affiliated companies

No further subjects will be dosed without thorough re-evaluation of the benefit-risk ratio, if severe non-serious adverse events considered as drug-related by the investigator are reported in 2 subjects of the same dose group or if at least one drug-related serious adverse event is reported.

2. The expected enrolment goals overall are not met
3. Violation of GCP, or the CTP by a trial site or investigator, disturbing the appropriate conduct of the trial
4. The sponsor decides to discontinue the further development of the investigational product.
5. Dose escalation will be stopped as soon as at least 2 subjects at one dose level on active drug showed relevant individual QT prolongation, i.e. absolute QT or QTc greater than 500 which has been confirmed by a repeat ECG recording or QTc increase of greater 60 ms from baseline in connection with absolute QT or QTc greater than 500 ms, which has been confirmed by a repeat ECG recording.
6. Dose escalation will be stopped if the C_{max} or AUC_{0-24} of at least 1 subject of one dose group increases above the following exposure thresholds or if the estimated systemic exposure (group gMean values) of the next dose level is expected to exceed a C_{max} of nM or an AUC_{0-24} of nM*h. In this case, one or two dose levels lower than the planned next dose level may be given, as long as the expected systemic exposure (group gMean values) of each dose is not expected to exceed the aforementioned thresholds.

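### The stated maximum human exposure and its safety margins are not what the escalation rule delivers: the dose about to be given is tested only on a predicted group mean, so individuals can exceed the limit

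*Protocol*

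**What the plan says.** **The limit as a maximum.** Protocol Section 2.1.2 introduces the Cmax and AUC0-24 limits with "The maximum human exposure to BI 1323495 in this trial will be limited to". It then attaches margins to them: at least 24 (Cmax) and 21 (AUC) against the exposures in the most sensitive species. Against the NOAEL in one 4-week study, "the maximum human exposure defined above provides safety factors of 16 and 10, respectively". Against the NOAEL in a further 4-week study, "this maximum human exposure provides safety margins of approximately 28 and 34, respectively". Section 2.3.3 repeats the limit with no reference to a mean: "drug plasma concentrations in this healthy volunteer trial should not exceed" the two figures.

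**The rule.** Section 2.1.2 allows the maximum dose only if observed individual values at a lower dose, "or predicted geometric mean values of C_{max} or mean AUC₀₋₂₄ do not exceed exposure limits defined above". Section 3.3.4.2, criterion 6, stops escalation if at least one subject of a dose group is above the threshold, or if the group gMean forecast for the next dose is above it. One or two dose levels below the planned next one may then still be given, "as long as the expected systemic exposure (group gMean values) of each dose is not expected to exceed the aforementioned thresholds".

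**The data behind the rule.** Section 7.3.4 provides individual values and geometric means of AUC0-24 and Cmax, and accepts data from as few as 2 active subjects of a dose group. Each full group has 6 active subjects (Section 3.1).

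**The concern.** A maximum exposure is a statement about the most exposed subject. A limit on a predicted group mean is a statement about the centre of the distribution. Section 2.1.2 uses the first to derive its margins and the second to decide whether the next dose may be given. The look-back at individuals does not close the gap, because it is triggered by a subject who has already passed the limit.

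This is a first-in-human trial in healthy men without therapeutic benefit, and Section 2.1.2 relies on the exposure margins when it calls the escalation adequate and safe. An ethics committee or regulator would naturally take 24/21, 16/10 and 28/34 as the smallest margins any subject could have. If the limit works on group means, the most exposed subjects have smaller ones, and the protocol does not say so.

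**Working it through.** **Inputs.** From the protocol: 6 active subjects per group; at least 2 active subjects in the preliminary PK look; steps of at most 1.5-fold at the higher doses (2.1.2); a last step from 3 to 4 tablets of one strength (4.1.1, dose groups 7 and 8), which is 4/3 = 1.33-fold; and the stated margins. The margins cannot be rebuilt, since the limits and animal exposures are blacked out, so they are taken as given.

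**Assumptions.** Log-normal exposure; between-subject CV of 20% to 50% (the documents give none); dose proportionality between adjacent doses; the same limit for individuals and for the gMean. Then σ = sqrt(ln(1 + CV²)).

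**1. Share of active subjects above the limit** = 1 − Φ(ln(limit/gMean)/σ).

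| CV | σ | gMean at limit | at 0.9 | at 0.8 | at 0.67 |
|---|---|---|---|---|---|
| 20% | 0.198 | 50% | 30% | 13% | 2% |
| 30% | 0.294 | 50% | 36% | 22% | 8% |
| 40% | 0.385 | 50% | 39% | 28% | 15% |
| 50% | 0.472 | 50% | 41% | 32% | 20% |

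With the gMean at the limit, P(at least 1 of 6 above) = 1 − 0.5^6 = 98.4% at any CV. At 0.8 of the limit, 1 − (1 − share)^6 gives 57%, 78%, 86% and 90% for CV 20%, 30%, 40% and 50%.

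**2. Margin for the most exposed subject, gMean at the limit.** The median of the highest of 6 solves Φ(z)^6 = 0.5, so z = 1.231 and the multiple of the limit is exp(1.231σ). Margins use the unrounded multiples.

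| CV | Highest of 6 (median) | AUC factor 10 becomes | Cmax factor 16 becomes |
|---|---|---|---|
| 20% | 1.28 × limit | 7.8 | 12.5 |
| 30% | 1.44 × limit | 7.0 | 11.1 |
| 40% | 1.61 × limit | 6.2 | 10.0 |
| 50% | 1.79 × limit | 5.6 | 8.9 |

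**3. How far the individual limb protects.** Suppose the next dose would have its gMean at the limit. The chance that no subject at the preceding dose was above the limit, so that this limb does not stop escalation, is Φ(ln(step)/σ)^n.

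| CV | 1.5-fold, n = 6 | 1.5-fold, n = 2 | 1.33-fold, n = 6 | 1.33-fold, n = 2 |
|---|---|---|---|---|
| 20% | 88% | 96% | 63% | 86% |
| 30% | 59% | 84% | 34% | 70% |
| 40% | 39% | 73% | 21% | 60% |
| 50% | 27% | 65% | 15% | 53% |

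**4. Both limbs together** (200,000 simulated runs per setting; forecast = step × observed gMean). A next dose whose true gMean equals the limit is allowed in 48%, 40% and 23% of runs at CV 20%, 30% and 50% (1.5-fold, n = 6), and in 41%, 28% and 14% for the 1.33-fold step. The gMean limb alone allows it in 50%.

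**5. Mixed summaries.** Section 2.1.2 pairs a geometric mean of Cmax with a mean AUC0-24; criterion 6 uses gMean for both. Under log-normality the arithmetic mean is sqrt(1 + CV²) times the geometric mean: 1.02 at CV 20% and 1.12 at CV 50%.

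**The case against.** The strongest reply is that the rule is not a group-mean rule. A reader might infer that any dose is admitted once its predicted gMean is not above the limit. The documents do not support that: one observed individual above the threshold also stops escalation. The gMean forecast is the only exposure test named in just one place, for the reduced doses that may follow once criterion 6 has triggered. The individual limb is a real safeguard, strongest where variability is high and the step small. It follows that the 98% figure and the factor of 5.6 must not be read together as the expected outcome: at CV 50% the boundary dose is often blocked beforehand.

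Three further replies have weight.

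- The limits are blacked out. Criterion 6 could hold one threshold for individuals and another for the gMean, and the Section 11 entry for amendment 1 mentions individual exposure limits. Section 2.1.2 applies one set of limits to both, which is why equality is assumed here, but it cannot be confirmed.
- Section 2.3.3 describes the figure as precautionary and preliminary, with a safety interim analysis and a substantial amendment required for further progression. That reads more like a trigger than a guarantee. Section 2.1.2 does not carry this softer wording into the sentence from which the margins are taken.
- The mean AUC0-24 wording may be shorthand for the geometric mean, as Section 7.3.4 suggests. That part is minor.

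These replies reduce the size of the problem. They do not remove the conflict: the individual limb responds only after the stated maximum has been exceeded, and nothing visible limits predicted individual exposure at the dose about to be given.

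**Conclusion.** The point holds as an inconsistency between the stated maximum with its margins (2.1.2, 2.3.3) and the rule meant to enforce it (2.1.2, 3.3.4.2 criterion 6). As written, the margins belong to the limit and not to the most exposed subject the rule permits.

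Its size depends on how close the gMean comes to the limit. A reader might infer that about half the active subjects exceed the limit at any permitted dose. That is true only in the boundary case; at 80% of the limit the share is 13% to 32%, and at 67% it is 2% to 20%. A reader might also infer that the limit or the margins are clinically inadequate. Nothing here shows that.

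The qualitative conclusion needs only some between-subject variability and a limit that applies to both individuals and group mean. The figures rest also on log-normality, an assumed CV of 20% to 50% and, for the individual limb, dose proportionality. If the blacked-out individual threshold differs from the gMean threshold, the figures change, and Section 2.1.2 would then need to say which of the two its margins refer to.

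**What to change.** Reconcile Section 2.1.2 (both the limit and the condition for the maximum dose), Section 2.3.3 and criterion 6 of Section 3.3.4.2 on one question: do the limit and the quoted margins refer to individual exposure or to the group geometric mean?

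If they refer to the group mean, stop describing the limit as the maximum human exposure, label 24/21, 16/10 and 28/34 as group-mean margins, and show beside them the smaller individual margins over a stated range of assumed CV. The range has to be assumed, because no human CV exists before dosing. If they refer to individuals, the protocol must make its account of the rule consistent with that. Which limit or rule applies is for the sponsor to decide, and none is proposed here.

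Use one summary measure for Cmax and AUC0-24 throughout.

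On the group-mean reading, the cost is a few sentences and a small table in the rationale, with no change to sampling, sample size or analysis. The price is that the individual margins shown will look less favourable than those now quoted.
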